i. This study is a prospective study so consent from the patient will be obtained prior to enrollment. To obtain consent, the physician will explain the purpose of the study, associated risk and benefits, and answer any additional questions or concerns the patient may ask. If patient decides to enroll in the study, the physician will provide them with the appropriate consent form and all signed forms will be in a securely locked filing cabinet.

c. Participants

i. Adult patients (age ≥18 years old) who have cirrhosis and present to RUMC with fluid retention (ascites, edema, or pulmonary effusions).

d. Inclusion/Exclusion Criteria

 Inclusion criteria: Adult patients (age ≥18 years old), diagnosis of cirrhosis and presents with fluid retention as defined as ascites, edema, or pulmonary effusions requiring diuresis.

ii. *Exclusion criteria*: Patients who are younger than 18 years of age or currently pregnant or who presents with a serum creatinine greater than 2 mg/dL will be excluded.

e. Outcomes

- i. *Primary outcome*: Urine output greater than or equal to 0.5 ml/kg/hour over 24 hours or reduction in weight defined as weight loss of 1 kilogram or greater in a 24-hour period. (While urine output is the best measure for diuretic efficacy, it can often be an unreliable measurement due to patient's not collecting urine properly. Therefore, changes in weight after initiation of diuretic therapy is often used as a surrogate marker for the efficacy of the diuretic therapy, regardless of patient weight at baseline. Several heart failure trials use a change in weight as the endpoint for assessing diuretic efficacy, and this endpoint is also commonly used in clinical practice. Therefore, that is why this endpoint was chosen for this study.)
- ii. **Secondary outcome:** Change in renal function as defined by a chance in serum creatinine from admission to discharge, hospital length of stay, 30-day readmission rates, and patient survival at 6 months and 1 year.

VI. Risk/Benefit Assessment

a. Potential Risks

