This study is a prospective trial however minimal risk to the patient is associated with participation in this study as he/she will be receiving one of two standard of care treatments at our center. Minimal risks associated with the study include experiencing common side effects from the FDA-approved medications used for treatment. The most common side effects of furosemide administered intravenously are low blood pressure, dizziness, headache, or irritation of the skin at the site of injection. In addition, the most common side effects of albumin administered intravenously are high blood pressure, headache, nausea/vomiting or irritation of the skin at the site of injection. There is also a potential risk for invasion of privacy since medical records will be accessed but all data will be de-identified to limit the chance of exposure of PHI.

b. Protection against risks

Physicians will be assessing patients in the study daily and will take precautions against the potential common side effects associated with the FDA-approved medications in this study as stated previously. Precautions include daily monitoring of patients through labs and physical examination and making medical interventions as deemed appropriate.

Data will be collected from the electronic medical record which will be de-identified and maintained in Research Electronic Data Capture (RedCap).

c. Potential benefits to subjects

Patients may benefit from taking part in this study. Based on experience with the use of furosemide (Lasix) and albumin in patients with similar conditions, researchers believe it

may be of benefit to people with cirrhosis. However, because individuals respond differently to therapy, no one can know in advance if it will be helpful for these patients. If the current therapy is not deemed helpful by the physician, the physician will start an alternative standard of care treatment for the patient.

d. Alternatives to participation

Patients may choose to not participate in this study. If participants choose to not participate in this study, the physicians will determine an alternative treatment plan for their fluid retention.

VII. Confidentiality of data and information storage

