a. Data collection will take place on a data collection tool, which will be separate from PHI and will not contain identifiers. RedCAP will be used for data collection and storage. Patient confidentiality will be maintained by recording only de-identified data onto the data collection form. Although the data collected and stored in REDCap will be exported for analysis, the exported data will contain no unique, patient-identifying information. Access will only be available to the research investigators.

Data collected from the electronic medical record at RUMC will include:

- 1. Patient demographics
- 2. Daily lab results including chemistry panel, INR, liver function tests, renal function tests
- 3. Physician's rating of patient's edema (if applicable)
- 4. Dose, frequency, and administration of furosemide (Lasix ®) and/or albumin

VIII. Analysis Plan

a. Statistical analysis will be performed with SPSS statistical package. Patient characteristics will be described using frequencies, means ± standard deviations or medians ± interquartile ranges. Student's t-test will be used to compare continuous variables. Comparisons between groups or categories will be made using chi-squared test. The threshold for statistical significance will be p<0.05.

IX. Literature Cited

- 2. American Association for the Study of Liver Diseases (AASLD): Practice guidelines for the management of adult patients with ascites due to cirrhosis 2012. Hepatology 57(4), 2013.

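### None of the side effects named in VI.a has an outcome, a listed data item or a between-arm analysis, so the tolerability of adding albumin would be compared only through creatinine, readmission and survival.

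*Combined protocol and SAP*

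**What the plan says.** Section VI.a lists expected side effects by drug. For furosemide: "side effects of furosemide administered intravenously are low blood pressure, dizziness, headache, or irritation of the skin at the site of injection". For albumin: "the most common side effects of albumin administered intravenously are high blood pressure, headache, nausea/vomiting", followed by irritation at the injection site.

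Section VI.b describes the protection offered: "Precautions include daily monitoring of patients through labs and physical examination and making medical interventions as deemed appropriate". It does not say that what is observed will be recorded as study data, graded or compared by arm.

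The primary outcome in V.e.i is urine output or weight loss. The secondary outcomes in V.e.ii are change in serum creatinine from admission to discharge, together with "hospital length of stay, 30-day readmission rates, and patient survival at 6 months and 1 year".

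Section VII.a opens its list with "Data collected from the electronic medical record at RUMC will include" and gives four items: demographics, laboratory results, a physician's edema rating, and study-drug administration. The laboratory item reads "Daily lab results including chemistry panel, INR, liver function tests, renal function tests". No item covers vital signs, symptoms, site reactions or adverse events.

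Section VIII provides a t-test for continuous variables and a chi-squared test for categories. It names no safety analysis.

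**The concern.** Both arms receive furosemide, and albumin is the only planned difference between them (V.a.i). The protocol itself says which unwanted effects to expect, yet the three sections that decide what the trial can report (outcomes, data list, analysis) do not mention them.

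Blood pressure is the clearest case. VI.a expects it to fall with furosemide and to rise with albumin, so the net effect of the combination cannot be reasoned out in advance and has to be measured. If it is not abstracted from the record, no later analysis can recover it.

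At stake is the reading of the efficacy result. A gain in diuresis with albumin could not be set against the side effects that the protocol attributes to it. The statement in VI.a that participation carries little risk could not be checked for those effects from the planned data.

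**Working it through.** **Step 1. Set the sections side by side.** The plan gives no safety figure to reproduce, so the main check is a comparison of text.

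| Effect named in VI.a | Named for | Outcome in V.e | Listed in VII.a | Analysis in VIII |
|---|---|---|---|---|
| Low blood pressure | furosemide | no | no | none named |
| High blood pressure | albumin | no | no | none named |
| Dizziness | furosemide | no | no | none named |
| Nausea/vomiting | albumin | no | no | none named |
| Headache | both | no | no | none named |
| Injection-site irritation | both | no | no | none named |

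All six effects are absent from all three places. Only blood pressure is named in opposite directions for the two drugs.

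**Step 2. What safety-relevant comparison remains.** Change in creatinine, 30-day readmission and survival at 6 months and 1 year are compared by arm, and each can show harm. A transient blood-pressure or tolerability effect could leave all of them unchanged. The chemistry panel is listed as data, but no electrolyte is named in an outcome.

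**Step 3. What collecting the data would deliver.** Inputs: a total of 150 (V.a.ii) and 1:1 allocation (V.a.i), hence 150/2 = 75 per arm, assuming equal arms and no loss. The 150 is taken as stated; how it was derived is a separate matter. The documents give no side-effect rates, so the rates below are assumptions shown as a range.

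*Zero events in one arm.* The one-sided 95% upper bound solves (1 − p)^75 = 0.05:

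1 − 0.05^(1/75) = 0.039, or 3.9%.

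*Power to detect a doubled rate,* two-sided alpha 0.05, n = 75 per arm, p2 = 2 × p1, p̄ = (p1 + p2)/2:

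power = Φ{[(p2 − p1) − 1.96 × SE0] / SE1}, with SE0 = √[2p̄(1 − p̄)/n] and SE1 = √[p1(1 − p1)/n + p2(1 − p2)/n].

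| p1 v p2 | SE0 | SE1 | Φ argument | Power |
|---|---|---|---|---|
| 2% v 4% | 0.0279 | 0.0278 | −1.24 | 11% |
| 5% v 10% | 0.0430 | 0.0428 | −0.80 | 21% |
| 10% v 20% | 0.0583 | 0.0577 | −0.25 | 40% |
| 20% v 40% | 0.0748 | 0.0730 | 0.73 | 77% |

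*Precision of a difference when both arms share rate p:* the 95% half-width is 1.96 × √[2p(1 − p)/75]. It is 4.5 points at p = 2%, 7.0 at 5%, 9.6 at 10% and 12.8 at 20%.

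The normal approximation is rough at the lowest rates, but the message does not depend on it. Large differences in common events would show. Modest differences in uncommon events would not.

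**The case against.** The strongest reply is that this is an efficacy study by its stated aim (III.a), that VI.a describes both arms as standard care with approved drugs, and that the hardest safety endpoints are already compared. Creatinine, readmission and survival arguably matter more to patients than headache or site irritation. This stands in part. A reader might infer that the trial makes no comparison of harms at all, and V.e.ii rules that out. A reader might also infer that the trial will issue a recommendation on albumin; the documents promise none.

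A second reply concerns the data list. Its opening words do not say that it is complete. It also omits urine output, weight, length of stay, readmission and survival, which are the trial's own outcomes. So the list does not support the inference that no safety data will be collected, and the laboratory part of the VI.b monitoring does reach the dataset. This reply stands against that stronger reading. It does not remove the gap: the omitted efficacy items are at least defined as outcomes, whereas the side effects appear in neither place. Their absence from V.e and VIII is the firmer evidence.

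Third, the general tests in VIII could be applied to sodium and potassium, so it cannot be said that these values will go unused. They are only not pre-specified, and VI.a does not name electrolyte disturbance as a side effect.

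Finally, a reader might take VI.a to say that the two drugs' side-effect profiles are opposite. That is true of blood pressure alone. Because both arms receive furosemide, the contrast is the combination against furosemide, not one drug against the other.

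**Conclusion.** The concern holds in a limited form. Six named side effects have no outcome, no listed data item and no planned between-arm analysis. Followed as written, the trial would inform the tolerability of adding albumin only through creatinine change, readmission and survival, and none of these measures a named effect. The efficacy question is unaffected. The point should be corrected because it limits what can be concluded and is cheap to repair before data are abstracted.

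The repair would give description, not proof of safety. The bound and power figures rest on 75 evaluable patients per arm and on assumed event rates; fewer patients would make both worse. A non-significant difference should not be reported as showing equal tolerability.

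**What to change.** 1. Add to the VII.a list, from first study dose to a fixed day common to both arms: the lowest and highest systolic blood pressure recorded each day, and a dated yes/no field for each side effect named in VI.a. A common window avoids giving longer-stay patients more time in which to have an event recorded.
2. Add to V.e.ii a descriptive safety secondary outcome by arm, covering hypotension and hypertension at cut-offs that the sponsor sets in advance, each named side effect, and lowest sodium and lowest and highest potassium from the chemistry panels already listed.
3. State in VIII that these will be reported as between-arm differences with 95% confidence intervals, and that absence of significance will not be read as absence of harm.

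Cost: a few more REDCap fields abstracted from the record and one table, with no new tests or visits. The main drawback is data quality. Routine notes record symptoms such as headache and dizziness unevenly, and no blinding is described, so knowledge of the arm could influence what is charted. Blood pressure and laboratory values should carry the comparison, with symptom counts as supporting information.

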Currently, there is only one randomized, controlled trial published in 1999 that compared the use of diuretics alone versus the combination of diuretics and albumin in cirrhotic patients.³ This was a single center conducted in Italy where the investigators used potassium canrenoate and furosemide as diuretics in combination with albumin (25%) 12.5 grams daily. The doses of diuretics used were per center protocol and based on patient clinical response. The results from their study showed that the cumulative rate of response to diuretic treatment of ascites was higher (90.5% vs. 74.7%) (p< 0.05) and length of hospital stay was shorter (p< 0.05) in the group of patients that received diuretics and albumin versus diuretics alone. Although the results were favorable with the use of albumin, the external validity of this study is minimal since it was a single center conducted in Italy in 1999.

III. Study Aims

a. The purpose of this single center, prospective study is to compare the efficacy of two strategies for diuresis in patients with cirrhosis, the use of furosemide (Lasix®) alone versus the combination of furosemide (Lasix ®) and albumin (25%).

IV. Administrative Organization

 a. All research regarding this project will be performed at Rush University Medical Center (RUMC). There will be no inclusion of outside study sites, laboratories, or data management centers.

V. Methods and Materials

- a. Trial Design and sample size
 - i. We will perform a single-center, prospective study with data collected as result of standard of care at RUMC. Patients who are 18 years of age and older, have diagnosed cirrhosis, and present to RUMC with fluid retention will be identified by the Hepatology and/or Surgery attending and be screened for inclusion in the study. Each patient will be randomized into one of the two cohorts and will have 50% chance of being placed into either cohort.
 Cohort 1 will receive furosemide (Lasix) 40 to 80 mg IVP BID for at least 48 hours and cohort 2 will receive combination of furosemide (Lasix) 40 to 80 mg
 - ii. A sample size of 150 patients for this study was estimated based on the previously published study by Gentilini P and colleagues.³ The estimation was based on a success rate of 70% in patients receiving diuretics alone and 90% in patients receiving diuretics plus albumin (alpha = 0.05; beta =0.25).

IVP BID and albumin (25%) 12.5 grams BID for at least 48 hours.

b. Process of Consent

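### The comparison of survival at 6 months and 1 year has no planned adjustment for baseline liver severity; one prespecified severity score would be a cheap and usually modest gain in precision

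*Combined protocol and SAP*

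**What the plan says.** Section V.e.ii lists "patient survival at 6 months and 1 year" among the secondary outcomes. Section VIII.a holds the whole inferential plan. For continuous outcomes a "t-test will be used to compare continuous variables", and for the rest "Comparisons between groups or categories will be made using chi-squared test". No regression, covariate, stratified test or time-to-event method appears, and no test is tied to survival by name.

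Section V.a.i says only that each patient "will have 50% chance of being placed into either cohort"; it mentions no stratification. Section V.a.ii gives the total: "A sample size of 150 patients for this study was estimated".

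The data list in VII.a includes "Daily lab results including chemistry panel, INR, liver function tests, renal function tests". The renal outcome in V.e.ii needs "serum creatinine from admission to discharge", so an admission creatinine will exist. Section V.d.ii limits its range: patients with "serum creatinine greater than 2 mg/dL will be excluded". INR and the liver tests are not restricted at entry.

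**The concern.** Alive or dead at a fixed time is a binary outcome, so the chi-squared test is the listed method that fits. Neither the allocation nor the analysis, as described, takes account of how sick patients are at entry. Baseline liver severity may well predict death over 6 to 12 months, and the trial will hold much of the laboratory data needed to measure it.

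Two things are at stake. The risk difference is estimated less precisely than the same data allow. And if one arm happens to receive sicker patients, the crude difference carries that imbalance with no planned way to remove it. Covariates chosen after the results are seen would not carry the same weight, so the choice has to be made in advance.

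**Working it through.** **The plan's own figure.** The plan gives no figure for survival. The only number used here is the total of 150, that is 75 per arm at 1:1. For the record, the primary outcome inputs (70% v 90%, alpha 0.05 taken as two-sided, beta 0.25) give n per arm = [1.960·√(2×0.8×0.2) + 0.674·√(0.7×0.3 + 0.9×0.1)]² / 0.2² = 54.6, so 55 per arm and 110 in total (130 with continuity correction). The gap from 150 does not affect this point.

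**Assumed inputs, none from the documents.** Control mortality 40% or 20%; conditional treatment odds ratio 0.45 or 0.7; one standard-normal baseline score with an odds ratio for death of 1.5, 2 or 3 per SD (c-statistic about 0.61, 0.68 and 0.76 at 40% mortality).

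**Model.** logit P(death) = a + log(OR treatment) × arm + log(OR score) × score, with 1,500 to 4,000 simulated trials per setting. The crude analysis is the chi-squared test. The adjusted analysis is the Wald test for arm in a logistic model with the score. The standardised risk difference is the average, over all 150 patients, of predicted risk under albumin minus predicted risk without it. Variance reduction = 1 − var(standardised) / var(crude).

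**Check against a closed form.** For 40% v 25% mortality, the crude SE is √[(0.24 + 0.1875)/75] = 0.0755; the simulation gave 0.075 to 0.076. Formula power is 50%; simulated power was 48–49%.

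**Results.**

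| Control mortality | Treatment OR | Score OR per SD | Power, crude to adjusted | Variance reduction |
|---|---|---|---|---|
| 40% | 0.45 | 2 | 53–54% to 57–58% | 7–10% |
| 40% | 0.45 | 3 | 45% to 52–54% | 18–20% |
| 40% | 0.7 | 2 | 17% to 17% | see below |
| 40% | 0.7 | 3 | 13% to 15% | see below |
| 20% | 0.45 | 1.5 | 41% to 39% | see below |
| 20% | 0.45 | 2 | 37% to 36% | see below |
| 20% | 0.45 | 3 | 33% to 35% | see below |
| 20% | 0.7 | 1.5–3 | 10–12% either way | see below |

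Ranges show repeated runs. Monte Carlo error on a power near 50% is at most √(0.25/1500) = 1.3 points. In the less favourable settings the variance still falls by about 4–17% at score OR 2 to 3, and by about 0–4% at score OR 1.5. Type I error is 4–6% for both analyses.

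As an equivalent sample size, a variance reduction of 4%, 10% or 20% corresponds to 150/0.96 = 156, 150/0.90 = 167 or 150/0.80 = 188 patients.

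**How favourable is the favourable case?** For a patient whose risk without albumin is 40%, the odds are 0.4/0.6 = 0.667. Then 0.667 × 0.45 = 0.30, a risk of 0.30/1.30 = 23%. That is a 17-point fall in mortality.

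**Chance imbalance.** The difference in mean score between arms has SD √(2/75) = 0.163. The probability that it exceeds 0.25 SD in either direction is 2[1 − Φ(0.25/0.163)] = 12.6%. At score log-odds of 0.6 and 1.0 per SD (OR 1.8 and 2.7), the crude risk difference moved by 0.077 to 0.203 per SD of imbalance across the mortality settings tried. At 0.25 SD that is 1.9 to 5.1 percentage points. The adjusted difference moved by at most 0.012 per SD, or 0.3 points.

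**One score or three covariates.** With 20% control mortality and OR 0.45, expected deaths are roughly 75 × 0.20 + 75 × 0.10 = 15 + 7.5, about 23 in all. Entering three covariates separately at 20% mortality gave variance reductions of about 0% (score OR 1.5), 3–5% (OR 2) and 9–12% (OR 3). With so few deaths, one score is the better choice.

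**The case against.** The strongest reply is that nothing here is an error. Randomisation makes the crude test valid, its type I error is about 5%, and chance imbalance is already part of its standard error. That stands. A reader might infer that the crude comparison is biased or confounded by severity. The documents do not support that reading: allocation is random, and the loss is in precision and in accuracy given the imbalance that actually occurs.

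The second reply is that the power gain depends on a favourable scenario. This also stands. A 17-point fall in one-year mortality is a large effect for a regimen specified only as lasting at least 48 hours, and the gain largely vanishes with fewer deaths or a smaller effect. Mortality at 6 months cannot exceed that at 1 year, so the earlier time point will tend to gain less. A reader might also infer that adjustment makes the survival comparison adequately powered. It does not: even in the favourable case adjusted power is only 52–58%.

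Third, the data are not quite guaranteed. Bilirubin is not named, a value from before randomisation is not promised, and the creatinine cap truncates one component of the score. These points qualify the claim that no new data are needed, but each can be dealt with in the wording.

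What survives is the reduction in variance when severity is at least moderately prognostic, and protection against a chance imbalance, at little cost.

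**Conclusion.** The point holds as an efficiency gain on a secondary outcome. The plan lists only unadjusted tests, describes no stratification by severity, and makes no use of severity markers that it largely collects. That the chi-squared test is meant for survival is an inference from its being the only listed test that fits.

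The size depends on how well the score predicts death. The variance of the risk difference falls by about 0–4% for a weak score and 4–20% for a moderate to strong one. The gain in power is 3–9 points in the favourable case and about −1 to +3 points otherwise; the 2-point fall in the weak-score row of the table is little more than simulation error. About one trial in eight would have a severity imbalance above 0.25 SD, where adjustment removes a shift of some 2 to 5 points or more from the crude difference.

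These figures assume 75 per arm with known vital status, a correctly specified single score, and mortality and effect sizes that the documents do not give. The creatinine cap may push the gain toward the lower end. Priority: consider.

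**What to change.** Add to section VIII.a:

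> Survival at 6 months and at 1 year will be compared by logistic regression with arm and one prespecified baseline severity score built from the last pre-randomisation INR, bilirubin and creatinine, reporting the standardised risk difference with a 95% CI (delta method or bootstrap). The unadjusted comparison is supportive.

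Write the formula of the score into the plan, and say what is done when a component is missing at baseline. In VII.a, name bilirubin and mark which laboratory values count as baseline.

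The cost is a few sentences, one regression for each time point, and an extra step for the interval, because the logistic output gives a conditional odds ratio and not a risk difference. If bilirubin and a pre-randomisation sample are already part of routine care, no new measurements are needed. If the score proves weakly prognostic, there will be little or no gain, or a slight loss.

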Cover Page: Study Protocol

Protocol Title: Comparison of furosemide alone versus the combination of furosemide and

albumin for diuresis in cirrhotic patients with fluid retention

NCT: 04216784

Document Date: 12/5/2019

I. Abstract:

a. A common complication of the progression of cirrhosis is fluid retention (ascites, edema, or pleural effusion). Loop diuretics are the treatment of choice for fluid retention in cirrhotic patients; however, many of these patients demonstrate diuretic resistance, requiring higher doses of the diuretics to achieve adequate diuresis. The cause of this diuretic resistance is hypothesized to be secondary to hypoalbuminemia which has led some providers to give human albumin in combination with loop diuretics to increase intravascular volume and facilitate diuresis. However, this practice remains controversial because minimal data exists to support its efficacy. The purpose of this study is to compare the efficacy of diuretics alone versus diuretics in combination with albumin in cirrhotic patients presenting with fluid retention.

II. Background and Significance:

a. Accumulation of fluid as ascites, edema, or pleural effusion is common in patients with advanced liver disease. 1 Typically, treatment of fluid retention is extrapolated from the practice guidelines by the American Association for the Study of Liver Diseases (AASLD) for the management of adult patients with ascites due to cirrhosis.² According to these guidelines, first line treatments for management of ascites are cessation of alcohol use (when applicable), restricting sodium and fluid intake, and using diuretics (such as loop diuretics). However, many patients with cirrhosis demonstrate diuretic resistance and require higher doses of these medications to obtain the desired clinical effect. Since hypoalbuminemia is postulated to be one of the causes of diuretic resistance in cirrhotic patients, some providers recommend giving albumin in combination with loop diuretics for the treatment of fluid retention. This recommendation developed from the current understanding of the pathophysiology of liver disease and its effect on intravascular space leading to fluid retention. Despite this common trend in practice, there remains minimal data that compares the efficacy of diuresis using diuretics alone versus the combination of diuretics and albumin.

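### The primary comparison is an unadjusted chi-squared test: valid, but it leaves out baseline albumin and creatinine, which could be pre-specified as covariates at little cost

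*Combined protocol and SAP*

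**What the plan says.** Section VIII (Analysis Plan) is one short paragraph. Patient characteristics are summarised descriptively, continuous variables are compared by t-test, and "Comparisons between groups or categories will be made using chi-squared test". It adds that "The threshold for statistical significance will be p<0.05". No adjusted model, stratified test or adjusted sensitivity analysis appears. The paragraph does not name the primary outcome. Section V.e defines that outcome as a yes/no response on urine output or weight loss, so chi-squared is the only listed method that fits it.

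On allocation, section V.a says only that each patient "will have 50% chance of being placed into either cohort"; no stratification factor is mentioned.

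On the candidate covariates:
- The Abstract states that "The cause of this diuretic resistance is hypothesized to be secondary to hypoalbuminemia".
- Section V.d excludes patients presenting with serum creatinine above 2 mg/dL, so a creatinine value must exist for every patient entered.
- The data list in section VII includes "Daily lab results including chemistry panel, INR, liver function tests, renal function tests". Renal function is explicit. Serum albumin is not named and is at most implied by the liver function tests.

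**The concern.** If low albumin contributes to diuretic resistance, as the protocol supposes, baseline albumin should help to predict who responds. Baseline renal function is a plausible second predictor. A test that leaves out prognostic baseline variables gives up some power. It also offers no planned answer if the arms happen to differ on them. With simple 1:1 allocation of 150 patients, the difference between arms in a standardised covariate has a standard deviation of √(2/75) = 0.163 SD, so a difference above 0.3 SD arises in about 7% of trials. In such a trial any adjustment chosen afterwards would be post hoc and open to challenge. Naming the covariates now avoids that.

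**Working it through.** **Inputs.** Section V.a gives a "success rate of 70% in patients receiving diuretics alone and 90% in patients receiving diuretics plus albumin", with "alpha = 0.05; beta =0.25", 150 patients in total and 1:1 allocation (75 per arm). Section II reports 74.7% v 90.5% from the cited earlier trial, used here only as a variant. Sidedness is not stated; two-sided 5% is assumed. The documents do not quantify any association between albumin or creatinine and response, so prognostic strength is an assumption and is varied below.

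**The plan's own sample size.** Pooled-variance formula:

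n per arm = [z(α/2)·√(2p̄(1−p̄)) + z(β)·√(p1(1−p1) + p2(1−p2))]² / (p1−p2)²

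With p̄ = 0.80: [1.960 × 0.5657 + 0.6745 × 0.5477]² / 0.04 = 1.478² / 0.04 = 54.6, so 55 per arm (110 in total). With continuity correction it is 65 per arm (130). The stated 150 is not reproduced. That is a separate matter; here 150 is taken as given.

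**Unadjusted power at 75 per arm.**
- 70% v 90%: (0.20 × √75 − 1.109) / 0.5477 = 1.138, giving 87.2%. Exact enumeration for uncorrected chi-squared gives 88.5%.
- 74.7% v 90.5%: (0.158 × √75 − 1.051) / 0.5244 = 0.605, giving 72.8%. Simulation gives about 74 to 75%.

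**Power with adjustment.** Simulation: 6,000 trials per scenario, 75 per arm, marginal rates held at 70% and 90%. Chi-squared is compared with the likelihood-ratio test for arm in a logistic model containing two baseline covariates. Simulation standard error is about 0.3 to 0.5 points.

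| Assumed log-odds per SD | AUC | Chi-squared | Adjusted | Gain (points) |
|---|---|---|---|---|
| 0 | 0.50 | 89.4% | 89.7% | about 0 |
| 0.25 | 0.57 | 87.6% | 88.2% | about 1 |
| 0.5 | 0.64 | 88.5% | 89.7% | about 1 |
| 0.75 | 0.69 | 88.6% | 90.6% | about 2 |
| 1.0 | 0.74 | 88.5% | 92.4% | about 4 |
| 1.5 | 0.82 | 88.3% | 95.0% | about 7 |

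A test based on the standardised risk difference had almost the same power as the likelihood-ratio test (89.5% at log-odds 0.5, 92.4% at 1.0). At 74.7% v 90.5%, with one covariate, power moved from about 74 to 75% to 76%, 80% and 83% at log-odds 0.5, 1.0 and 1.5.

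**If the association exists only in the furosemide-alone arm** (4,000 trials, main-effects model):
- 70% v 90%: 89.0% v 89.3% at log-odds 0.5, and 88.2% v 89.3% at 1.0.
- 74.7% v 90.5%: 75.6% v 75.6%, and 74.4% v 75.4%.

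The gain is 0 to 1 point in these runs, and 0 to 2 points across all simulations of this case.

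**Type I error.** In the tabulated simulation, chi-squared rejected in 5.0 to 5.5% of null trials and the adjusted test in 5.3 to 6.0%. Across all simulations the ranges are 4.5 to 5.5% and 5.0 to 6.2%.

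**Given an unlucky imbalance** (one covariate, common slope, log-odds 0.5 / 1.0). These figures come from small subsets of the simulated trials and carry a few points of error.
- Imbalance above 0.3 SD (0.3/0.163 = 1.84, about 7% of trials), true rates 70% v 70%: chi-squared rejects in 7.4% / 11.5%, the adjusted test in 4.4% / 6.6%.
- Imbalance above 0.2 SD against the albumin arm (0.2/0.163 = 1.22, about 11% of trials), rates 74.7% v 90.5%: power is 67% / 52% unadjusted and 79% / 77% adjusted.

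**Model size.** Expected failures are 75 × 0.30 + 75 × 0.10 = 22.5 + 7.5 = 30, for three terms (arm and two covariates).

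**The case against.** The strongest reply is that nothing is broken. An unadjusted chi-squared test is valid in a 1:1 randomised trial. Randomisation balances covariates in expectation, and the test's error rate already allows for chance imbalance. This stands. A reader might infer that the lack of adjustment or stratification biases the comparison; the documents and the simulated type I error do not support that.

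A reader might also infer that the trial is underpowered without adjustment. On the plan's own rates it is not: about 87 to 88% against a target of 75%. Power drops to about 73 to 75% only at the earlier trial's rates, which are not the planning assumption.

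Other objections also stand:
- The larger gains need a strong slope common to both arms. If low albumin causes resistance and one arm receives albumin, the slope may lie mainly in the furosemide-alone arm, where adjustment adds little.
- A creatinine entry limit does not show that creatinine predicts response, and it truncates the range at 2 mg/dL.
- The adjusted likelihood-ratio test is slightly liberal, which accounts for part of the smaller gains.
- Serum albumin is not an eligibility item, so some baseline values could be missing. A complete-case model would then drop patients.
- Logistic regression gives a conditional odds ratio; a standardised risk difference takes a further step.

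These points limit the size of the benefit and call for care in specification. They do not remove the case for adjustment: simulated power was no worse when the covariates were useless, and error control averaged over all randomisations does not help to interpret the single one obtained.

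**Conclusion.** The point holds as a recommended improvement in efficiency, not as an error in the plan. The planned analysis does not use two baseline measurements, one tied to the protocol's own rationale and the other known at entry. Under assumed prognostic strengths, adjustment adds about 0 to 2 power points for weak to moderate covariates or a slope in the furosemide-alone arm only, and about 3 to 5 points for a strong common slope. Larger gains, such as 7 points, need a very strong covariate (AUC about 0.82), which nothing in the documents suggests. There is no loss if the covariates predict nothing.

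Protection against an unlucky imbalance matters most in the minority of trials where one occurs, and it too depends on how prognostic the covariates are. The conclusion assumes two-sided testing, 75 analysed per arm, that chi-squared is meant for the primary outcome, and that baseline serum albumin is or can be collected.

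**What to change.** Before any outcome data are seen, amend section VIII as follows:

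1. Make the primary analysis a logistic regression of response on arm, with the last pre-dose serum albumin and serum creatinine as continuous covariates.
2. Report the standardised risk difference with a 95% CI, and state how its variance is obtained (delta method or bootstrap).
3. Keep all randomised patients, using a stated simple imputation for any missing baseline covariate.
4. Retain chi-squared as the unadjusted sensitivity analysis.
5. Optionally, add one treatment-by-baseline-albumin term, labelled exploratory.

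In section VII, name serum albumin as a collected baseline item.

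The cost is a few sentences and one logistic model, which SPSS can fit, plus the extra variance step. Eligibility and sample size need not change. The slight excess in type I error (about 5 to 6%) should be acknowledged in the plan.
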